3.2 ENROLMENT AND FOLLOW-UP

We aim to start enrolment from November 2020 (pending ethics approval) and enrol participants for approximately twelve months or until the sample size is met. The enrolment period may be extended in the event of disruptions to clinic services due to COVID-19. Where feasible, all children and adolescents meeting the inclusion criteria and attending the participating clinics during this period will be invited to take part; where this is not possible, a convenience sample of children and adolescents (e.g. those attending clinic on a specified day of the week) should be invited. The invitation to participate should be independent of the patient's probability of having been exposed to COVID-19.

Participants will be considered lost to follow-up for the purposes of this study if they have not provided the second blood sample by 13 months after the enrolment date.

Participants enrolled in the EPPICC Paediatric Study or CTAAC will continue to be followed up as part of the ongoing study.

Logs will be kept of the number of children and adolescents declining the invitation to participate, with reasons for refusal where available.

3.3 STUDY INTERVENTIONS

There are no interventions in this study. Venous blood will be taken by qualified healthcare personnel according to standard techniques used in routine care at the same time as routine blood sampling.

3.4 LABORATORY TESTING

Where sites are conducting serological testing as part of standard care, venous blood samples taken at each site will be transported to the laboratory(ies) routinely carrying out antibody testing for that site. Samples will be analysed with the tests used by each site in routine practice according to manufacturers' instructions or, if in-house tests are used, local SOPs/protocols.

At sites not offering routine serological testing, arrangements should be made with local laboratories for testing. There is strong preference for tests for IgG against the viral spike protein as data suggests this has the longest half-life; however, it is recognised that there may be local considerations influencing the range of tests available across settings and results from other tests will be considered.

Where possible, antibody test results will be reported both categorically (e.g. positive, negative, equivocal) and quantitatively (e.g. antibody titre). Results will be transferred securely as described in Section 4.2.

3.5 DISCONTINUATION OR EARLY WITHDRAWAL OF PARTICIPANTS

Participants (or their parents/carers) may withdraw from the study at any time without providing a reason.

Participants wishing to withdraw from the study will be offered two options:

1. Participants may withdraw from active follow-up (i.e. future study procedures) within this study but allow the retention and use of data already collected, and further linkage with other data sources as described in the Participant Information Sheet.
2. Participants may withdraw completely from the study, in which case all data and samples collected (if not already tested) would be destroyed and no further follow-up or linkage would take place as part of this study.

Should a participant (or their parent / carer) lose the capacity to consent, they will be withdrawn from active follow-up and their data / samples retained and included in data linkages. Participants who withdraw for any reason will not be replaced.

All withdrawals will be recorded in the study database.

3.6 SAFETY REPORTING

In this observational setting the safety reporting will follow and will be notified according to the ICH GCP and legal requirement under current national legislation.

The only procedure in this study which is additional to standard care is a blood draw, to be performed in a healthcare setting by healthcare professionals following standard methods. Safety risks to the participant are therefore minimal. Additionally, where possible, residual blood from samples taken for routine clinical care will be used, thus avoiding the need for participants to undergo a separate blood draw specifically for this study.

4 DATA COLLECTION AND MERGING

4.1 DATA COLLECTION

Collection of core data items in the main EPPICC Paediatric study for sites included in the EPPICC network is described in the main EPPICC Paediatric protocol; this includes demographic data and clinical, therapeutic, laboratory and outcome information relating to HIV, COVID-19 and multi-system inflammatory syndrome in children (MIS-C). Several identified or potential risk factors for SARS-CoV-2 infection / disease / death are included in or can be derived from the main EPPICC dataset, e.g. age, sex, ethnicity, body mass index, CD4 count, viral load, ART regimen, HCV / HBV status. These data are extracted from clinic records and submitted as part of the main EPPICC study following the study SOP, and will be linked to data collected through the serology study. If a participant is included in EPPICC and additional data are available subsequent to the most recent data submitted to EPPICC, this additional data will also be collected.

Sites which are not members of the EPPICC network will submit equivalent data relating to the time of the two study visits for CLWHIV and HIV-uninfected adolescents (Table 2).

Table 2: Summary of data to be collected at each study visit from CLWHIV and HIV-uninfected adolescents

Domain	Variables	CLWHIV	HIV-uninfected adolescents*
Study identifiers	Participant ID number, site ID	✓	✓
Demographic	Date of birth, sex, ethnicity/country of origin	✓	✓
HIV	Mode of acquisition of infection, date of diagnosis, disease stage (current and at ART initiation)	✓	
Therapeutic	Initial ART regimen and start dates, recent ART history (from start of 2020)	✓	
Co-infections	Co-infections (TB, HCV, HBV)	✓	✓
Clinical	Weight (current and at ART initiation where applicable), height (current and at ART initiation where applicable), pregnancy	✓	✓
Laboratory	Absolute CD4 counts and percentage, HIV RNA (Current and at ART initiation where applicable)	✓	
COVID-19	Suspected or confirmed COVID-19 and MIS-C diagnosis; viral genomic data; symptoms, treatments and outcomes; receipt of COVID-19 vaccines	✓	✓
SARS-CoV-2 serological test	Date of test; type of test used; result (categorical and quantitative)	✓	✓
Co-morbidities	Diabetes; asthma; cancer; renal disease / impairment; autoimmune / inflammatory conditions; history of shielding; smoking status; current or previous tuberculosis disease or infection; sickle cell anaemia; history of solid organ transplant	✓	✓
Other	Follow-up status, death, cause of death, reason for study drop-out	✓	✓

* CTAAC only

Additionally, a short questionnaire will be completed by the participant (or their parent / carer) to provide information about potential exposures to COVID-19, including diagnoses in household members and known contacts and uptake of COVID-19 vaccine.

For any participant with a record of a suspected or confirmed COVID-19 or MIS-C diagnosis, the cohort will be asked to complete an additional case record form providing details of the diagnosis (e.g. clinical features, hospital admissions, treatments and outcomes).

4.2 DATA MERGER METHODS

Individual cohorts will collect data from medical records in clinics and enter data from patient questionnaires electronically. Cohorts will then send electronic datasets to the MRC CTU at UCL, using a format and method defined in the study Standard Operating Procedure (SOP) and/or a Research Electronic Data Capture (REDCap) database. Transfer of data to the MRC CTU at UCL takes place using Galaxkey or an equivalent secure method such as UCL's REDCap server. Data are then uploaded into a customised database.

Submitted data undergo a range of logic and consistency checks. Any identified potential errors or inconsistencies are investigated through discussion between the EPPICC Paediatric Data Manager, statisticians at the MRC CTU, and individual cohorts. This may involve several rounds of queries with resubmission of data over a period of several months. When data from each site have been sufficiently cleaned, the datasets are combined into a single database.

Data may be submitted by cohorts in real time (if using REDCap) or at the end of the last patient follow-up. An initial data submission of a small number of patients may also be done early in the data collection period, to allow identification and resolution of any technical issues.

5 QUALITY ASSURANCE & CONTROL

5.1 RISK ASSESSMENT

The Quality Assurance (QA) and Quality Control (QC) considerations are based on a formal Risk Assessment, which will acknowledge the risks associated with the conduct of the study and how to address them with QA and QC processes. QA includes all the planned and systematic actions established to ensure the study is performed and data generated, documented and/or recorded and reported in compliance with the principles of Good Clinical Practice and applicable regulatory requirements. QC includes the operational techniques and activities done within the QA system to verify that the requirements for quality of the study-related activities are fulfilled. This Risk Assessment will lead to the development of a Monitoring Plan.

5.2 CENTRAL MONITORING AT MRC CTU AT UCL

Recruitment will be monitored by weekly submission of numbers enrolled via email or REDCap. This will be discussed at regular teleconferences during which any issues with recruitment will be discussed. Initially, these will be held every 2-4 weeks but may become less frequent as the study progresses.

The MRC CTU Study Team will review submitted electronic data for errors and missing data points, and consistency with previous data submissions where appropriate. An extensive series of error checks will be performed. Data queries are sent to cohorts for resolution. All submitted data, and the merged dataset, will be stored on secure servers and backed up daily. MRC CTU at UCL handling of data will follow the principles of the UK Data Protection Act.

6 STATISTICAL CONSIDERATIONS

6.1 SAMPLE SIZE

The total sample size is 1150, with provisional numbers eligible by cohort summarised in Table 3. Allowing for 70% participation, the target sample size can be met within the participating cohorts. At some sites within EPPICC, participants will receive SARS-CoV-2 serological tests as part of routine care or within an ongoing research study, and a repeat test will be offered as part of this study approximately six months after (no less than 3 and up to 13 months) the first sample; however both sets of results will be collected in this study. At other sites and in South Africa, both tests will be part of this study.

In addition, some sites may be able to test stored samples taken for other purposes and not previously tested for SARS-CoV-2 antibodies. In these cases, this would be considered the first test and the participant would have one additional test as part of this study approximately six months (no less than 3 and up to 13 months) after the first sample date.

Table 3: Provisional numbers of eligible participants (aged <25 years) per cohort

Cohort	Number of eligible participants	
	CLWHIV	HIV-uninfected adolescents
Belgium	74	0
Greece	22	0
CoRISPES (Spain)	250	0
CoRISPE-Cat (Spain)	50	0
Sweden	85	0
Ukraine	170	0
United Kingdom	442	0
EPPICC Total	1093	0
South Africa	400	50-100
Total	1493	50-100

Assuming an overall anti-SARS-CoV-2 prevalence of 10%, similar to that reported for children aged 10-19 years in Geneva, Switzerland [3], the sample size would result in a 95% confidence interval of +/- 2% in Europe and +/-3% in South Africa.

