Shupyk National Medical Academy of Postgraduate Education, Kiev
Perinatal Prevention of AIDS Initiative, Odessa

United Kingdom / Ireland (CHIPS and CHIPS+ cohorts):

[name] (CHIPS and CHIPS+ overall PI) University College London, UK

Site PIs:

[name], [name] Great Ormond Street Hospital for Children NHS Foundation Trust, London (CHIPS)

[name], [name] Guy's and St Thomas' NHS Foundation Trust, London (CHIPS / CHIPS+)

[name] North Manchester General Hospital (Northern Care Alliance NHS Group), Manchester (CHIPS)

[name], [name] University Hospitals Birmingham NHS Foundation Trust, Birmingham (CHIPS, CHIPS+)

[name] Imperial College Healthcare NHS Trust, London (CHIPS / CHIPS+)
[name], [name] King's College Hospital NHS Foundation Trust, London (CHIPS, CHIPS+)

[name], [name] St George's University Hospitals NHS Foundation Trust, London (CHIPS, CHIPS+)

SUMMARY OF STUDY

SUMMARY INFORMATION TYPE	SUMMARY DETAILS
Acronym	EPPICC- SARS-CoV-2 antibody study
Long Title of Study	Prevalence of SARS-CoV-2 antibodies in children, adolescents and young adults living with HIV in Europe and South Africa
Version	3.0
Date	18 May 2021
MRC CTU at UCL ID	EPPICC SARS-CoV-2
REC #	17493/002
Study Design	Serial point prevalence survey
Setting	HIV clinics across Europe and South Africa.
Type of Participants to be Studied	Children and young adults living with HIV
Aim	To describe the prevalence and distribution of antibodies to SARS-CoV-2 in children and young adults living with HIV in Europe and South Africa
Sponsor	Penta Foundation
Number of Participants to be Studied	1150
Duration	18 months
Funder	Research grant from ViiV Healthcare. The MRC CTU at UCL is supported by the Medical Research Council programme grant MC_UU_12023/26. EPPICC is funded by grants from the Penta Foundation. CTAAC is funded by the National Institutes of Health, USA.
Chief Investigator	[name]

LAY SUMMARY

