1.2 OBJECTIVES

Primary objective:

- To estimate prevalence of SARS-CoV-2 antibodies in the paediatric and adolescent HIV population and how this changes over time, overall and by key age groups and regions

Secondary objectives:

- To assess factors associated with presence of SARS-CoV-2 antibodies (including demographic factors, antiretroviral treatment, HIV-associated factors or co-morbidities and exposure to household members with COVID-19, receipt of COVID-19 vaccine)
- To estimate the incidence of changes in antibody status to SARS-CoV-2 and associated factors

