2.5 NUMBER OF PATIENTS

A total of 1150 participants will be included. This comprises 650 participants to be enrolled from the EPPICC cohorts in Europe and 500 from the South African CTAAC cohort, which will include ~50-100 HIV uninfected participants as a comparator group. The sample size calculation is described in Section 6.1.

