3 STUDY PROCEDURES

3.1 STUDY DESIGN

This is a serial point prevalence survey of representative samples of children and adolescents attending routine HIV care in the participating clinics and cohorts, with repeat antibody testing at baseline (study entry) and approximately 6 months after study entry (Table 1), and in some clinics further long-term follow-up through linkage to data collected in an ongoing longitudinal cohort study. In South Africa approximately 50-100 HIV-uninfected adolescents enrolled in the ongoing CTAAC cohort will be invited to participate in this study as a comparator group.

Eligible participants who are interested in joining the study will be asked for their consent to participate if aged ≥ 16 years or as per local legal requirements. For participants aged <16 years, consent of their parent/carer will be sought as per legal requirements. Assent will be sought from children and adolescents aged 10 years and older, depending on local ethics requirements. Potential participants and their parents / carers should be allowed at least 5-10 minutes to consider whether or not to take part; where possible, it may be helpful to give patients copies of the participant information sheet while they wait for their appointment.

Data collection will be conducted at HIV clinics during routine visits in clinical care (in the European cohorts) or planned study visits (in CTAAC, for both CLWHIV and HIV-uninfected adolescents), and no additional study visits will be required.

At entry to the study the participant will give a venous blood sample for a SARS-CoV-2 antibody test (the exact test used will depend on local clinical practice). An additional serum sample will be taken at the same time as a routine blood draw and leftover sample will be used if possible. At the next scheduled routine HIV clinic/study visit approximately 6 (no less than 3 and up to 13) months later, a repeat venous blood sample will be collected for a second antibody test. At each visit, participants (or their parents/carers) will be given a COVID-19 questionnaire, asking short questions about any COVID-19 diagnoses in themselves or among household members and other possible exposures to the virus. All study procedures will be carried out following local COVID-19 guidelines.

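### At the stated 70% participation, Table 3 yields 315–380 participants in South Africa, not the 500 that section 2.5 requires

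*Combined protocol and SAP*

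**What the plan says.** The Summary row headed "Number of Participants to be Studied" reads 1150. Section 2.5 splits this figure: "650 participants to be enrolled from the EPPICC cohorts in Europe and 500 from the South African CTAAC cohort". It adds of the South African part: "which will include ~50-100 HIV uninfected participants as a comparator group".

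Section 6.1 ties the total to a table of available patients: "The total sample size is 1150, with provisional numbers eligible by cohort summarised in Table 3". It then says: "Allowing for 70% participation, the target sample size can be met within the participating cohorts". No region is named for the 70%. The caption and column heading of Table 3 describe its counts as eligible participants. For South Africa the row shows 400 living with HIV (CLWHIV) and 50–100 HIV-uninfected.

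Section 3.1 uses the same range for a third purpose: "In South Africa approximately 50-100 HIV-uninfected adolescents enrolled in the ongoing CTAAC cohort will be invited to participate in this study". So 50–100 appears as the number included (2.5), invited (3.1) and eligible (Table 3).

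On precision, section 6.1 assumes 10% prevalence and says "the sample size would result in a 95% confidence interval of +/- 2% in Europe and +/-3% in South Africa". It does not say whether the South African figure covers all participants or CLWHIV only.

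**The concern.** A participation rate below 100% applied to a pool of at most 500 cannot give 500 participants. The sentence in 6.1 and the split in 2.5 therefore conflict in South Africa, whatever happens in Europe.

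The target has a practical role. Section 3.2 runs enrolment for about twelve months or until the sample size is reached, and section 5.2 monitors recruitment weekly. A regional target above its own expected yield is a poor yardstick for either. The primary objective is "To estimate prevalence of SARS-CoV-2 antibodies in the paediatric and adolescent HIV population and how this changes over time", overall and by region, so the number of South Africans living with HIV sets the precision of a primary estimate. The HIV-uninfected comparator group is also found only in South Africa.

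**Working it through.** **Inputs**
- Targets: Europe 650, South Africa 500, total 1150 (section 2.5).
- Participation: 70%, no region named (section 6.1).
- Eligible in Europe: 74 + 22 + 250 + 50 + 85 + 170 + 442 = 1093, which agrees with the Table 3 subtotal.
- Eligible in South Africa: 400 CLWHIV plus 50–100 HIV-uninfected = 450–500 (Table 3).
- Prevalence 10%, 95% confidence (section 6.1).

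**Step 1. The plan's own precision figures.** Half-width = 1.96 × √(0.1 × 0.9 / n).
- n = 650: 2.31 points, stated as 2.
- n = 500: 2.63 points, stated as 3.

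Both reproduce after rounding. At n = 400 (CLWHIV only) the result is 2.94, which also rounds to 3.

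**Step 2. Expected enrolment = participation × eligible.**

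| | 70% of everyone | 70% of CLWHIV, all HIV-uninfected join | Target |
|---|---|---|---|
| Europe | 0.7 × 1093 = 765 | 765 | 650 |
| South Africa, CLWHIV | 0.7 × 400 = 280 | 280 | – |
| South Africa, HIV-uninfected | 0.7 × (50 to 100) = 35–70 | 50–100 | – |
| South Africa, all | 315–350 | 330–380 | 500 |
| Total | 0.7 × (1543 to 1593) = 1080–1115 | 0.7 × 1493 + (50 to 100) = 1095–1145 | 1150 |

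The South African shortfall is 500 − 350 = 150 to 500 − 315 = 185 on the first reading, and 500 − 380 = 120 to 500 − 330 = 170 on the second.

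**Step 3. Participation that the targets need.**
- South Africa: 500/500 = 100% at the top of the range and 500/450 = 111% at the bottom. At 70%, 500/0.7 = 714 eligible would be needed.
- Europe: 650/1093 = 59.5%, so there is room to spare.
- Overall: 1150/1593 = 72.2% to 1150/1543 = 74.5%.

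**Step 4. The reading in which 70% applies to Europe only.** If all listed South African participants enrol, the pool is 765 + 450 = 1215 to 765 + 500 = 1265, above 1150. South Africa itself still gives 450–500.

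**Step 5. Precision at the lower South African numbers**, by the formula in step 1.

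| South African group | n | Half-width (points) |
|---|---|---|
| CLWHIV, all listed | 400 | 2.9 |
| CLWHIV at 70% | 280 | 3.5 |
| All participants, lowest yield | 315 | 3.3 |
| All participants, highest yield | 380 | 3.0 |

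For CLWHIV in both regions together, 1045 (0.7 × 1493) and 1050 (650 + 400) both give 1.8.

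**The case against.** The strongest defence is that the 70% was meant for European clinics, and that the South African row is planned enrolment under a loose label. Several things support it. The row's upper end, 400 + 100, equals the 500 in section 2.5 exactly. A range of 50–100 looks more like a quota than a count from an existing cohort. CTAAC participants are seen every six months at planned study visits (Background; section 3.1), so uptake there could well exceed that in routine clinics. On this reading the sentence in 6.1 is true of the total, which is all that it literally claims.

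The defence does not clear the text. Nothing available limits the 70% to Europe, Table 3 calls its counts eligible, section 3.1 says the 50–100 will be invited, and section 2.1 requires consent in CTAAC too. Section 2.4 (Participating cohorts) was not in the text available for this review and might explain the row. Even with the defence granted in full, 500 is reached only if 100 HIV-uninfected adolescents join; with 50 it is 450.

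Two further objections stand. The table counts are provisional, so an overall gap of 5 people (1145 against 1150) on the kinder 70% reading carries no weight. The effect on precision is also small. Section 3.2 allows enrolment to be extended, but more time does not enlarge a fixed pool.

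**Conclusion.** The text is wrong as written; severity minor. The South African target of 500 does not follow from the plan's own inputs. At 70% the yield is 315–350, or 330–380 with every HIV-uninfected adolescent enrolled. If the 70% does not apply there, the listed 450–500 reaches 500 only at its upper end.

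A reader might infer that the total of 1150 cannot be reached, or that 1145 is a ceiling. The documents do not support that. It holds only if 70% applies to every CLWHIV participant, and the Europe-only reading gives 1215–1265. A reader might also infer that the stated precision fails or that the estimates are compromised. Neither follows: no estimate is biased, and ±3 points still holds after rounding for all South African participants at 315–380. What changes is the half-width for South Africans living with HIV, from 2.9 points at 400 to 3.5 at 280, and only if the 70% applies to them.

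The mismatch in the available text is certain. How far South African enrolment would fall short is not, because it depends on an intention that this text does not state.

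**What to change.** In section 6.1, state to whom the 70% applies and whether the South African row of Table 3 is an eligible pool or planned enrolment. Then follow one branch.

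- **If 70% applies in South Africa:** restate its target as 330–380 (280 CLWHIV plus 50–100 HIV-uninfected), and the total with Europe at 650 as 980–1030. If the 70% also applies to the HIV-uninfected, these become 315–350 and 965–1000.
- **If it does not:** state the participation assumed in CTAAC, correct the Table 3 label if the row is planned enrolment, and restate 500 as 450–500, with a total of 1100–1150. Those figures imply that everyone listed enrols, so the text should say so.

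In either case carry the figures into section 2.5 and the Summary, say which population the South African half-width covers, and give it for CLWHIV at the resulting number (3.5 points at 280; 2.9 at 400).

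The cost is a few sentences and numbers, and possibly one table label. No extra patients or procedures are needed; the stated figures become slightly less favourable.

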1 BACKGROUND

As of 14 October 2020, the WHO European region had reported over 7 million COVID-19 cases and almost 250,000 deaths [1]. At the time of initiating this study, although the number of reported cases has been lower in the African region (just over 1.2 million), likely due to both later arrival of the pandemic and incomplete reporting, over half of these have been in South Africa and over 18,000 COVID-19 deaths have been reported in the country [1].

Seroprevalence studies provide estimates of the percentage of the population that has either been infected with SARS-CoV-2 (the virus which causes COVID-19) or vaccinated against the virus, based on evidence of antibodies against the viral spike (S) or nucleocapsid (N) proteins. However, few published studies have included data from children and adolescents [2, 3]. The prevalence of antibodies to SARS-CoV-2 in children in (pre-vaccination) population studies has been estimated as ~3-4% in those aged 0-19 in Spain by mid-May 2020 [2], and 0.8% in 5-9 year-olds and 9.6% in 10-19 year-olds in Geneva by early May 2020 [3]. In England, seroprevalence in 1-24 year olds has been estimated as 5.2% (95% credible interval 3.2-7.8%) based on samples collected between May and August 2020 [4]. Whilst uncertainties remain about the extent and duration of protection that antibodies may provide, measuring seroprevalence is a first step towards understanding the proportion of a population that remains susceptible to infection and therefore the potential risk of future outbreaks.

There are currently limited and inconsistent data on the epidemiology of SARS-CoV-2 and COVID-19 in people living with HIV. The studies published to date have presented data on COVID-19 amongst adults living with HIV [5-11] but it remains unclear to what extent HIV affects the risk of infection, disease, severe disease or death. Some studies suggested that there may not an association between HIV and COVID-19 severity or mortality [5], whilst others suggest increased mortality amongst adults with COVID-19 co-infected with HIV compared to the HIV-uninfected population, even after adjustment for co-morbidities and other factors [11, 12]. These studies have not included children.

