2.2 EXCLUSION CRITERIA

Children and adolescents are ineligible if they:

- Are taking part in a COVID-19 / SARS-CoV-2 vaccine study at enrolment

However, should a participant who is enrolled in the EPPICC-SARS-CoV-2 study subsequently join a COVID-19 / SARS-CoV-2 vaccine study or receive a COVID-19 / SARS-CoV-2 vaccine, these are not reasons for exclusion from this study. Data will be collected on vaccine receipt and participation in vaccine studies.

At the time of writing this protocol, COVID-19 / SARS-CoV-2 vaccines are being made available at different speeds across the participating countries, so there is a possibility that study participants may receive a vaccine over the course of this study. Participation in this study must not influence or delay the choice to receive a COVID-19 vaccination, either through participation in a trial or through a vaccination programme.

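### Section 6.1: 70% participation in the Table 3 pool does not yield the 1150 target, least of all in South Africa, and the stated precision rests on a pre-vaccination 10% prevalence

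*Combined protocol and SAP*

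**What the plan says.** Section 6.1 makes two quantitative statements about the sample of 1150. On feasibility: "Allowing for 70% participation, the target sample size can be met within the participating cohorts". On precision, at an assumed overall prevalence of 10%: "the sample size would result in a 95% confidence interval of +/- 2% in Europe and +/-3% in South Africa".

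Section 2.5 splits the 1150 into 650 from Europe and "500 from the South African CTAAC cohort, which will include ~50-100 HIV uninfected participants as a comparator group". Table 3 in Section 6.1 lists provisional eligible numbers: 1093 in Europe, and in South Africa 400 living with HIV plus 50-100 HIV-uninfected. The primary objective (Section 1.2) is prevalence in the paediatric and adolescent HIV population, overall and by age group and region.

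Section 6.1 ties the 10% to a population survey of 10-19 year-olds in Geneva. Section 1 gives that survey's result as 9.6% by early May 2020 and places it among pre-vaccination studies. The same section describes seroprevalence as the share of a population that "has either been infected with SARS-CoV-2 (the virus which causes COVID-19) or vaccinated against the virus". Section 2.2 notes that "there is a possibility that study participants may receive a vaccine over the course of this study" and keeps such participants in. Section 3.4 strongly prefers IgG tests against the spike protein. Section 6.1 does not mention vaccination.

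**The concern.** The two half-widths are the only quantitative justification that Section 6.1 gives for the sample size, and the 70% sentence is the only assurance that the sample can be reached. A reader will take both at face value.

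Two things do not fit. First, the South African target is as large as, or larger than, the number of eligible people listed for South Africa, so it cannot be compatible with 70% participation. The 500 also includes HIV-uninfected comparators, who do not contribute to the primary estimate. Second, the prevalence behind the half-widths predates vaccination, while the current version measures antibody from infection or vaccination. The absolute half-width grows with prevalence up to 50%, so the stated precision may not describe the estimate that the study will report, particularly at the second visit.

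**Working it through.** **Inputs.** Planned n: 650 in Europe; 500 in South Africa including about 50-100 HIV-uninfected, hence 400-450 living with HIV (Section 2.5). Prevalence 10%, participation 70%, and eligible numbers 1093, 400 and 50-100 (Section 6.1 and Table 3).

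**1. Reproducing the stated half-widths.** Half-width = 1.96 × √(p(1−p)/n), with p = 0.10.

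- Europe, n = 650: 1.96 × √(0.09/650) = 2.31 points, which rounds to 2.
- South Africa, n = 500, 450, 400: 2.63, 2.77 and 2.94 points, all of which round to 3.

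The exact (Clopper-Pearson) method gives 2.38 for 650 and 3.06 for 400, with the same rounding. The stated figures therefore follow from the planned numbers at whole-point precision.

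**2. The 70% statement against Table 3.**

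- Total eligible: 1493 + 50 = 1543 to 1493 + 100 = 1593. At 70%: 0.70 × 1543 = 1080 to 0.70 × 1593 = 1115. The shortfall against 1150 is 35 to 70. Meeting 1150 needs 1150/1593 = 72% to 1150/1543 = 75%.
- Europe: 0.70 × 1093 = 765, above the 650 planned; only 650/1093 = 59% is needed.
- South Africa: eligible 400 + 50 = 450 to 400 + 100 = 500, against a target of 500. That requires 100% participation at the upper end and cannot be met at the lower end. At 70%: 0.70 × 450 = 315 to 0.70 × 500 = 350, of whom 0.70 × 400 = 280 are living with HIV.

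The 1080-1115 already counts Europe's surplus. If Europe stops at its planned 650, the total is 650 + 315 = 965 to 650 + 350 = 1000.

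**3. South African precision at 70%.** For n = 280: 1.96 × √(0.09/280) = 3.51 points, which no longer rounds to 3. For reference, a half-width of 3.0 needs 1.96² × 0.09/0.03² = 384.2, so 385 participants. Rounding to 3 needs fewer than 3.5 points: 1.96² × 0.09/0.035² = 282.2, so 283.

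**4. Sensitivity to prevalence.** The documents give no value to replace 10%. The other prevalences below are assumptions. Half-widths are in percentage points.

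| Prevalence | Europe, n = 650 | South Africa, n = 400 | South Africa, n = 280 |
|---|---|---|---|
| 5% | 1.7 | 2.1 | 2.6 |
| 10% | 2.3 | 2.9 | 3.5 |
| 20% | 3.1 | 3.9 | 4.7 |
| 30% | 3.5 | 4.5 | 5.4 |
| 50% | 3.8 | 4.9 | 5.9 |

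The European figure stops rounding to 2 above a prevalence of about 12%, and the South African figure (n = 400) stops rounding to 3 above about 15%.

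**The case against.** A reader might infer from the 2.31 that the half-widths are an arithmetic slip, since an unrounded 2.0 points in Europe needs 1.96² × 0.09/0.02² = 864.4, so 865 participants. The documents do not support that: the figures are given in whole points, and the planned numbers round to them. Nor does the South African 3% require all 400 eligible participants living with HIV. As shown above, 385 gives 3.0, and 283 or more still rounds to 3; 280 misses by three participants. This part of the defence stands in full.

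It can also be said that the 70% speaks to feasibility and was never meant to reduce the planned n, and that applying it evenly would help Europe (765, half-width 2.13). That is fair, and it is why the 3.5 points describes what follows if 70% is achieved; it is not the plan's stated n. But it is precisely as a feasibility statement that the sentence fails.

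Table 3 is labelled provisional, and its South African row (400 plus up to 100) may simply restate the target, with the 70% intended for Europe alone. That is possible. However, the table presents every row as eligible participants, and the sentence speaks of the participating cohorts together.

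On prevalence, the 10% is openly an assumption. The Background also cites lower values, such as 5.2% for ages 1-24 in England, at which the intervals would be narrower. First tests may be earlier results or stored samples from March 2020 onwards (Section 3.1), and Section 6.2 already plans estimates by vaccine receipt. All of this stands, so it cannot be said that the intervals will be wider than stated. What remains is that the one value used is pre-vaccination, that second samples may be taken up to 13 months after the first, and that Section 1 names people with HIV aged 16 and over in the UK as a vaccination priority group. The UK supplies 442 of the 1093 eligible Europeans (40%).

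**Conclusion.** The concern holds on two limited points.

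First, the statement that 1150 can be met at 70% participation is untrue on Table 3. The shortfall is 35 to 70 overall. In South Africa, 70% gives 315 to 350 against 500, with 280 living with HIV and a half-width of 3.5 points. This rests on reading Table 3 as eligible people and the 70% as applying to every cohort, which is what the text says.

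Second, the half-widths are shown only at a pre-vaccination prevalence, in a version that also counts vaccine-induced antibody. Prevalence may be higher, but that is an assumption.

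A reader might go further and infer that the intervals will be about twice as wide as stated. That compares the 50% worst case with rounded figures or with a reduced n. At fixed n the ratio of 50% to 10% prevalence is √0.25/√0.09 = 0.50/0.30 = 1.67, and nothing in the documents says that 50% will be reached. Even the widest value in the table, 5.9 points, leaves a usable interval. The calculations use the simple binomial formula with no allowance for clustering by clinic. The point deserves correction but does not threaten the study.

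**What to change.** Change wording in Section 6.1:

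1. Reconcile the 70% sentence with the South African target of 500 and the total of 1150. Either state the participation that each region needs (59% in Europe; all or more of the listed pool in South Africa), or revise the provisional eligible numbers or the target. If the target changes, Section 2.5 and the study summary must match.
2. Base the South African precision on participants living with HIV, and give one decimal at 10% prevalence: Europe ±2.3% (n = 650); South Africa ±2.9% (n = 400) and ±3.5% (n = 280).
3. Say that the 10% is a pre-vaccination value, and add half-widths at higher assumed prevalence. At 30% and 50% these are 3.5 and 3.8 in Europe; 4.5 and 4.9 in South Africa at n = 400; 5.4 and 5.9 at n = 280.

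A precision figure for the comparison by HIV status would be an optional addition; the plan states none, so there is nothing to correct there.

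The cost is a less favourable stated precision. No extra participants and no change to the analysis are needed.
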